1. DULCET STUDY PROTOCOL SYNOPSIS

Title:	Dulcet Study: A non-significant risk clinical investigation of the VibratoSleeve, a therapeutic ultrasound (TUS) phased array, for patients with ischemic and neuroischemic diabetic foot ulcers (DFU).
Design:	Prospective, single arm, open label clinical trial to evaluate the feasibility of TUS in the treatment of DFU, with three different treatment levels Low, medium and high acoustic intensities, corresponding to different peak negative pressures)
Device Name and Intended Use:	VibratoSleeve is an array of single element ultrasound transducers, driven in a phased manner, and held in place externally by an adjustable sleeve. In this study, device experts will use the VibratoSleeve in a clinic setting and will evaluate for evidence of an increase in distal limb TcPO ₂ in adult subjects with ischemic and neuroischemic DFU.
Visit Schedule:	Visits will occur at screening (baseline data) and at three in-clinic treatment sessions, each separated by at least a 1-week interval.
Study Objectives:	The objectives of this study are: 
 Establish a safety profile for both the procedure and the VibratoSleeve TUS for the treatment DFU. Gather initial evidence of the treatment and immediate post-treatment efficacy of the VibratoSleeve TUS in DFU subjects. Request subject usability feedback: comfort, tolerability, and human factors of the VibratoSleeve assessed by questionnaire and certain human and operator factors associated with the use of the device.
Number of Subjects and Defined Point of Enrollment	Up to twelve subjects will be required for treatment and evaluation. The defined point of enrollment will be the time at which the patient signs the Informed Consent Form (ICF) to undergo screening procedures to ascertain eligibility. An estimated 50% of enrolled subjects may not satisfy all inclusion/exclusion criteria. Therefore, up to twenty-four subjects may have to be enrolled to generate twelve evaluable subjects qualified for both treatment and evaluation.

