Inclusion Criteria	
 Presence of at least one DFU (grade 0 or 1 according to the University of Texas classification). Diagnosis of diabetes mellitus. Diagnosis of PAD that meets at least one of the following conditions: 
 Ankle-brachial index (ABI) of < 0.9 in the same limb as the DFU Toe Brachial Index (TBI) ≤ 0.6 OR Toe Blood Pressure ≤ 50 mmHg Documented history of PAD for a minimum of 3 calendar months prior to time of enrollment Aged ≥ 22 years
Exclusion Criteria	
 Rutherford 6 stage PAD. Active DFU infection. End-stage renal disease on dialysis.

	
 4. HbA1c > 11%. 5. Planned PAD revascularization. 6. Prior stenting in posterior tibial, anterior tibial or peroneal artery. 7. Re-vascularization procedure within 30 days prior to enrollment in the study. 8. History or diagnosis of severe chronic venous insufficiency or mixed arterio-venous disease. 9. Acute limb ischemia within 30 days prior to treatment. 10. History or diagnosis of deep venous thrombosis below the knee in treatment leg. 11. Any conditions that, in the opinion of the investigator, may render the patient unable to complete the study or lead to difficulties for patient compliance with study requirements, or could confound study data. 12. Patient's enrollment in another investigational drug or device study that has not completed the required primary endpoint follow-up period.
Safety Endpoint	To evaluate the overall safety of the VibratoSleeve TUS device for the treatment of PAD, the Principal Investigator will undertake a detailed assessment of all procedure- and/or therapy-related adverse events.
Efficacy Endpoints	
 • Transcutaneous Oxygen Pressure (TcPO₂). • Perfusion rate, as measured with the FlowMet device (Medtronic). • DFU tissue oxygenation (StO₂) and hemoglobin content (HbT2), as measured with the Clarifi device (Modulim).

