Treatment	
Each TUS treatment will be provided at a clinic following debridement and ulcerated wound assessment. Each subject will receive three levels of TUS treatment (low, medium, and high acoustic intensities, corresponding to different peak negative pressures). Each of the three treatments will occur on separate dates, spaced at least one week apart. The duration of each treatment level will be 90-minutes.
 
The VibratoSleeve will be applied to the posterior calf (proximal to the TUS) using water-based acoustic coupling gel by trained clinical trial staff, and TUS delivered using Vibrato's custom generator. This study is designed to address acute changes in perfusion with each of the three TUS treatments.

Statistical Hypothesis	Statistical hypotheses will not be applied in this pilot study. Information collected during the study may be used to support a 510(k) application as well as to select the endpoints and determine sample sizes for future trials.
Study Duration	The Sponsor expects the trial to last eight months from the time the first subject enrolls until the time of the last follow-up visit.

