2. STUDY FLOW CHART

3. SCHEDULE OF EVENTS

Table 1. Data collection requirements

Activity	Screening / Baseline (Day 0)	1 st Treatment Session (Days 0+)	2 nd Treatment Session (1 st Treatment + ≥7 Days)	3 rd Final Treatment Session (2 nd Treatment + ≥7 Days)
Informed Consent	X			
Demographics & Medical Drug History	X			
Clinical Evaluation & Rutherford and University of Texas Classification and Calf Circumference (mm)	X			
I/E Criteria	X			
ABI/TBI	X*	X	X	X
Transcutaneous Oxygen Pressure (TcPO ₂)		X	X	X
Perfusion of the foot: FlowMet and Clarifi devices		X	X	X
Vital Signs		X	X	X
Subject Questionnaire		X	X	X
Adverse Events	X	X	X	X
Protocol Deviations	X	X	X	X

*Only required if needed for PAD documentation (see inclusion criteria #3)

All treatment visits will be completed within 3 months of the first treatment session

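### Does the protocol leave open whether perfusion is read before or after debridement, so that a debridement effect could pass for a treatment effect?

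*Protocol*

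**What the plan says.** All places are in the Protocol.

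- Section 1, Treatment, gives the aim: "This study is designed to address acute changes in perfusion with each of the three TUS treatments". It gives the order within a session: "Each TUS treatment will be provided at a clinic following debridement and ulcerated wound assessment". It also gives the length: "The duration of each treatment level will be 90-minutes".
- Section 1, Study Objectives, names the period of interest: "Gather initial evidence of the treatment and immediate post-treatment efficacy of the VibratoSleeve TUS in DFU subjects".
- Section 1, Device Name and Intended Use, says that the study "will evaluate for evidence of an increase in distal limb TcPO" (the subscript 2 follows).
- Section 1, Efficacy Endpoints, lists the measures by name: TcPO2, FlowMet perfusion rate, and "DFU tissue oxygenation (StO₂) and hemoglobin content (HbT2), as measured with the Clarifi device (Modulim".
- Section 3, Table 1, has a row for TcPO2 and a row "Perfusion of the foot: FlowMet and Clarifi devices". Each has one mark at each of the three treatment sessions and none at screening.
- Section 1, Statistical Hypothesis, says that no hypotheses are applied and that the data may be used to "select the endpoints and determine sample sizes for future trials".

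**The concern.** An acute change needs a reference reading. Table 1 has no perfusion reading at screening, so the reference has to come from the treatment session itself. That session contains several distinct moments: before debridement, after debridement but before ultrasound, during the 90 minutes, and just afterwards. One untimed mark does not tell them apart.

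Debridement acts on the ulcer, and the Clarifi measures are read on ulcer tissue. If some or all reference readings came before debridement, its effect would be added to the change credited to ultrasound. The trial has one arm and no sham session, so the two effects could not be separated afterwards, and no analysis plan can recover a reading that was never taken. Because the data may inform endpoint choice and sample size for later trials, a distorted mean or SD of the change would carry forward.

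**Working it through.** **1. What the visible text fixes.** Set side by side, the statements give an order and a target:

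| Place in the Protocol | What it settles |
|---|---|
| Synopsis, Treatment | Debridement and wound assessment come first, ultrasound second |
| Synopsis, Treatment | The quantity of interest is the acute change with each treatment |
| Synopsis, Study Objectives | Readings of interest fall during and immediately after treatment |
| Table 1 | All three devices are used at every treatment session, none at screening |

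The change belongs to the ultrasound treatment, and debridement is over before that treatment starts. The reference that fits this description is a same-session reading after debridement and before ultrasound. No sentence points to a reference before debridement, or to a different order in different sessions.

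**2. What one mark in Table 1 means.** The columns of Table 1 are visits. A mark says that the activity takes place at that visit. It does not say that it takes place once, nor at which minute. A visit-level table is therefore compatible with readings before, during and after treatment.

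**3. The only derived figure in the document.** Enrolment: 12 / (1 − 0.5) = 24, which agrees with the stated twenty-four. It has no bearing on this point. No alpha, power, effect size or SD is stated that the reading order could affect.

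**4. How large the effect would be under other orders.** This is an illustration. The debridement shift d, in units of the SD of the within-session change, is an assumption; the protocol gives neither its size nor its direction. Take n = 12 at one level, no ultrasound effect, df = 11, t(0.975) = 2.201.

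- Bias in the mean change = p × d, where p is the share of reference readings taken before debridement.
- For p = 1, the probability that the 95% interval lies wholly above zero is 1 − F(2.201), with F the noncentral t distribution with 11 df and noncentrality d × √12.
- For p = 0.5 (each reference before debridement with probability one half), the same probability comes from 400,000 simulated studies.

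| Assumed shift d | d × √12 | p = 0 | p = 0.5 | p = 1 |
|---|---|---|---|---|
| 0.25 | 0.87 | 2.5% | 6% | 12% |
| 0.5 | 1.73 | 2.5% | 12% | 35% |
| 1.0 | 3.46 | 2.5% | 29% | 88% |

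The p = 0 column is the order that the text supports, and there the bias is 0 × d = 0 whatever d may be. The other columns need a reading order that nothing in the protocol indicates. If debridement lowered the reading, the distortion would run the other way and hide an increase.

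**5. What spelling the order out would change.** Recording a pre-treatment and a post-treatment reading would only write down what the stated aim already requires. Demanding a reading at a set minute during treatment on all three devices would be new work for staff who read only before and after: up to 3 devices × 3 sessions × 12 subjects = 108 further device readings. The objective speaks of efficacy during treatment but does not ask for that from every device.

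**The case for a change.** The best case for the concern is that reading times belong in the schedule of events. Staff at the bedside follow that schedule, and a missing post-debridement reference cannot be rebuilt later by any statistical method. The objective names the periods during and after treatment but never mentions a pre-treatment reading. Screening is described as supplying baseline data, yet Table 1 has no perfusion reading there. With no sham session, the design offers no protection if the order is wrong.

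Part of this stands. No visible sentence states the order of the device readings within a session, and a reference that was not taken is lost. The figures in the table above are also correct for the assumptions they use.

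The rest does not amount to an error in the plan. The visible text is a synopsis and a table by visit, where order by the minute is not usually found. Section 2 is a study flow chart, a natural place for this order; its content could not be seen, so it cannot be called silent. The harm needs two things that the protocol does not suggest: a reference taken before debridement, and a sizeable debridement shift in the direction of benefit. Its reach is also limited. It would matter most for Clarifi and less for distal-limb TcPO2, the only measure whose increase the synopsis names. The comparison between the three intensity levels is less affected if every session follows the same order.

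**Conclusion.** The concern does not hold. The protocol puts debridement before ultrasound, aims at the change with each ultrasound treatment, and looks at the period during and just after it. Followed sensibly, that gives a same-session reference between debridement and treatment, for which the debridement bias is zero. What the visible text lacks is an operating detail, not a correct statement in place of a wrong one.

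The rates of up to 88% describe a hypothetical departure from that order with an assumed shift of a full SD. They also use an interval-excludes-zero criterion in a pilot that applies no hypotheses, so they are no measure of a defect in this plan.

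The conclusion rests on two assumptions: that the unseen flow chart does not place the reference reading before debridement, and that all sessions follow one order. A flow chart or site procedure showing otherwise would reopen the point, chiefly for the Clarifi measures.

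### Does letting the same twelve pilot subjects inform both endpoint choice and later sample sizes build an inflated effect into the plan?

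*Protocol*

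**What the plan says.** All relevant text is in the Protocol, section 1 (Synopsis).

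- **Statistical Hypothesis row:** "Statistical hypotheses will not be applied in this pilot study". The same row says that the information *may* support a 510(k) submission and may also serve "to select the endpoints and determine sample sizes for future trials".
- **Number of Subjects row:** "Up to twelve subjects will be required for treatment and evaluation". Twelve is a ceiling, and no alpha, power, effect size or SD is given for it.
- **Efficacy Endpoints row:** four measures in three bullets, namely TcPO₂, FlowMet perfusion rate, and Clarifi StO₂ and hemoglobin content. TcPO₂ comes first; no order of importance is stated.
- **Device Name and Intended Use row:** device experts "will evaluate for evidence of an increase in distal limb" TcPO₂. No other measure is named there.
- **Treatment row:** every subject receives all three levels, on separate dates.

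The protocol gives no rule for choosing an endpoint, does not mention choosing a level, and does not say which pilot quantity would enter a later sample-size calculation.

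**The concern.** One sentence gives one small dataset two jobs: choosing what to measure next and deciding how many subjects that will need. Four measures at three levels give 4 × 3 = 12 estimates from at most 12 subjects. If the largest is chosen because it is the largest, and then used as the planning effect, the data have been used twice and the effect is overstated.

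At stake would be a follow-on trial that is much too small. With assumed correlations of 0.3 between measures and 0.5 between levels, and a true standardised effect of 0.3 everywhere, the median best-of-twelve estimate is 0.78. That implies about 13 subjects where about 87 are needed, and 13 subjects have 17% power. With no true effect at all, the best estimate still averages 0.45 SD, and there is a 21% chance that at least one of the twelve reaches a nominal one-sided p below 0.025. The possible use in a 510(k) submission adds to the worry.

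**Working it through.** **The plan's own arithmetic.** Twelve evaluable subjects at 50% screen failure: 12 / (1 − 0.5) = 24, which matches the stated enrolment ceiling. The twelve itself has no power calculation behind it, as expected where no hypothesis is tested.

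**Inputs for the selection effect.** From the protocol: n = 12 (the ceiling), four measures, three levels. Assumed, because the protocol gives none of these: paired change scores, multivariate normal; a true standardised effect d equal in all twelve cells; correlation 0, 0.5 or 0.8 between measures and between levels; a next trial at two-sided 0.05 and 80% power. There were 20,000 replicates.

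**Formula.** Next-trial size N = ((1.96 + 0.8416) / d̂)², rounded up, where d̂ is the effect carried forward (floored at 0.05, with N at least 4). Actual power comes from the noncentral t at the true d.

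**Results for true d = 0.5, correlation 0.5:**

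| How the next trial is sized | Mean effect carried | Median N | Mean power |
|---|---|---|---|
| One measure and level named beforehand | 0.54 | 30 | 0.70 |
| TcPO₂, best of three levels | 0.75 | 16 | 0.51 |
| Best of four measures at one level | 0.81 | 14 | 0.47 |
| Best of all twelve | 1.04 | 8 | 0.30 |
| Set difference of 0.5 | none | 32 | 0.78 |

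Last row: (2.8016 / 0.5)² = 31.4, so N = 32. The power of 0.78 takes the SD as known.

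**Range.** For best of twelve at true d = 0.5, the carried effect is 1.16, 1.04 or 0.87 at correlation 0, 0.5 or 0.8, with mean power 0.22, 0.30 or 0.43. For best of four it is 0.90, 0.81 or 0.72, with mean power 0.38, 0.47 or 0.55.

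**What the numbers depend on.**

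1. *The selection rule.* The sentence speaks of endpoints, not levels, so at most four candidates have support in the text. Twelve is an extrapolation.
2. *Equal true effects.* If every cell has the same effect, picking the maximum picks only noise. If one cell truly dominates (1.2 against 0.1 to 0.6 elsewhere, correlation 0.5), mean inflation falls to 0.19 and mean power is 0.58.
3. *The comparator.* Even with no selection, an effect estimated from 12 subjects gives mean power of about 0.67 to 0.70 over the effects tried. Part of the shortfall from 80% is therefore the pilot's size. The 95% limits on the SD show the same imprecision: √(11/χ²) runs from 0.71 to 1.70 times the estimate.
4. *The sizing rule.* The last row of the table carries no observed effect forward, so choosing the largest effect cannot inflate it. The protocol's sentence is as compatible with that row as with any other.

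**The text against the premise.** For the harm to follow, the protocol would have to say that the endpoint with the largest observed effect will be chosen and that this observed effect will size the next trial. It says neither. Endpoints can also be chosen on measurability, variability or tolerability. The nominal p-value risk has nothing to attach to, since no test is planned.

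**The case for a change.** The best case for the concern is that it survives the narrow reading. With correlation 0.3 between measures, best of four at one level, and a true effect of 0.3, the median carried effect is 0.58. That implies about 24 subjects instead of 87, with 29% power. At a true effect of 0.5 the median is 0.82, implying about 12 instead of 32, with 35% power. One measure and level named beforehand gives a median of 0.31 for a true 0.30, and a trial sized on that median has about 78% power. At the median, then, the loss is due to selection. Both uses stand in one sentence, the endpoint list is unranked, and a best-looking result from an open-label, uncontrolled study could reach a 510(k) file.

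The arithmetic stands, and so does the observation that the list has no ranking. What fails is the step from permission to plan: every figure is conditional on a rule that the protocol does not contain. The 510(k) point likewise presumes that a selected result would be submitted alone, which the protocol does not say. Only the protocol was available here. Ranking of exploratory endpoints, confidence intervals and limits on the SD commonly belong in a SAP, so their absence is no defect.

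Nor is the obvious remedy free. Fixing TcPO₂ at the end of the 90 minutes would narrow a pilot meant to help choose endpoints, and the Study Objectives row also covers effects just after treatment. Reasonable statisticians could differ on that trade.

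**Conclusion.** The concern does not hold. Informing endpoint choice and sample size is an ordinary purpose of a feasibility pilot, and the protocol states it as an option, tests nothing, and already points to TcPO₂ as the measure of interest. Followed as written, it yields descriptive results that are sound for that purpose; no estimate or conclusion of this trial is biased by the sentence.

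The size of any harm lies wholly in a later protocol. At an assumed true effect of 0.5 and correlation 0.5, there is no inflation from the pilot if that trial is sized on a set difference. Inflation is 0.81 − 0.50 = 0.31 if the best of four measures is carried forward, and 1.04 − 0.50 = 0.54 if the best of twelve is. These figures rest on equal true effects in all cells, normal change scores and a paired next trial, none of which the protocol specifies. The caution is worth remembering when that trial is designed, but it is no fault in this plan.

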2. STUDY FLOW CHART

3. SCHEDULE OF EVENTS

Table 1. Data collection requirements

Activity	Screening / Baseline (Day 0)	1 st Treatment Session (Days 0+)	2 nd Treatment Session (1 st Treatment + ≥7 Days)	3 rd Final Treatment Session (2 nd Treatment + ≥7 Days)
Informed Consent	X			
Demographics & Medical Drug History	X			
Clinical Evaluation & Rutherford and University of Texas Classification and Calf Circumference (mm)	X			
I/E Criteria	X			
ABI/TBI	X*	X	X	X
Transcutaneous Oxygen Pressure (TcPO ₂)		X	X	X
Perfusion of the foot: FlowMet and Clarifi devices		X	X	X
Vital Signs		X	X	X
Subject Questionnaire		X	X	X
Adverse Events	X	X	X	X
Protocol Deviations	X	X	X	X

*Only required if needed for PAD documentation (see inclusion criteria #3)

All treatment visits will be completed within 3 months of the first treatment session
